	The PI and study staff will provide any technical assistance regarding journaling for the participants and a direct number and email address for any additional issues that may potentially arise.
Intervener Training	Because all training content explained at baseline is uniform, and the journaling will be recorded in the journals at least twice a week, there will be no deviance in the provision of the program across participants.
Treatment Delivery & Receipt	A study-specific protocol will be developed and explicitly followed. Dosing (times per week the participant completed journals and practice) will be meticulously tracked by evaluating: the number of journal entries at least twice a week and the number of words written per journal entry in the hardcover journal. The journal will be given at week 0, and the journal will be collected after week 8 during the final appointment.
	We will limit the entries to six memories, with a target goal of 10-15 minutes spent journaling, and no set schedule (having entries occur in the morning or evening). The study staff will provide a weekly email reminder to enter a journal entry at least twice a week.
Treatment Enactment	We will follow participants from week 0 to week 8 to determine sustained use of the intervention (intermediate output).

Gratitude Intervention: The proposed study builds on Emmons and McCullough's original gratitude journaling intervention.⁴⁹ The original intervention, mostly undergraduate psychology students, did not include a goal-setting exercise and conducted daily gratitude journaling. However, prior cardiovascular health studies have found that interventions pairing optimism and gratitude with education and systematic goal-setting related to physical activity led to more physical activity, fewer hospital readmissions, and improved levels of inflammatory

Protocol Page 4 of 12

biomarkers.³⁶ Therefore, this study will pair the use of goal setting and physical activity education and to reduce the burden of journaling for cancer survivors and the participants will journal at least twice a week. During the initial session, the Principal Investigator or research assistant will provide a journal kit and an educational physical activity brochure to assist in setting 1-2 physical activity goals during the study period.

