Data Collection and Study Procedures: After screening for eligibility and collection of verbal consent, we will schedule an in-person appointment to collect baseline data, including collection of a blood sample (see Table 1 for measures and variables to be collected). Before the appointment, we will send demographic and cancer history questionnaires and self-report instruments (listed below) to participants for review. Informed written consent will be obtained at the in-person appointment, and an electronic survey will be sent following completion of the first appointment. After baseline (T1) data collection, participants will be randomized to either the gratitude journaling intervention or attention control group in a 1:1 ratio using online randomization software (http://randomization.com), and block randomization to ensure equal distribution between groups. The PI will inform participants of their group assignment and provide intervention details. The research assistant and biostatistician will be blind to group allocation. Participants will begin their daily intervention within 1 week of completing T1 data collection. They will also be scheduled for their T2 data collection appointment, which will occur 8 weeks after the start of the intervention and will include the same measures as baseline excluding the demographic and cancer history questionnaires. Data will be stored in Qualtrics on a secure university server and password protected with the assistance of the Biostatistics Core.

Blood Collection, Processing, and Storage: Blood samples will be obtained by a registered nurse or phlebotomist using the CTSI's standard protocol at the UF Clinical Research Center. After a ten-minute rest period, up to 10 ml of blood will be drawn. No more than two attempts will made to obtain blood samples with any participant. Blood samples will be collected, processed and stored with the OAIC Metabolism and Translational Science Core in the UF Clinical Research Center.

Table 1. Study Measures.

Outcome (Time Points)	Measure/Description
Demographics (T1)	Age, sex, education, marital status, body mass index; cancer- and treatment-related variables
	including time since diagnosis, cancer stage, grade and other disease-related variables including
	hormonal and HER2 status, surgical type, chemotherapy, radiotherapy, and cancer treatment.
Dispositional gratitude	The Gratitude Questionnaire-6 (GQ-6), a well-validated, self-administered 6-item scale, is

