Separate two-by-two mixed-effects general linear models (GLMM),⁵⁴ comprised of effects for treatment, time, and treatment-by-time interaction, will be used to estimate effect sizes for each of the outcome variables. The distribution of residuals will be evaluated for the tenability of model assumptions, and, where necessary, remedial measures such as Box-Cox transformations will be applied. CONSORT guidelines for intent-to-treat principles will be used for hypothesis testing to manage missing data related to attrition. We will determine differences between groups using t-tests.

6. Possible Discomforts and Risks: Protection of Human Subjects

PI Version: 09/21/2022

According to federal regulations and NIH policy, applications that propose to involve human subjects must address risks to human subjects (human subject characteristics, involvement and design; sources of materials; and potential risk); adequacy of protection against risks (recruitment and informed consent and

Protocol IRB version 03.09.04 protections against risk); potential benefits of the proposed research (are potential risks to subjects reasonable in light of anticipated benefits?); the importance of the knowledge to be gained; and a data- and safety-monitoring plan/board. We address each of these requirements below.

Risks to Human Participants

Inclusion/Exclusion Criteria. Table 2 lists study inclusion/exclusion criteria. Exclusion criteria are designed to prevent inclusion of participants who would experience discomfort or harm during collection of blood or other data and to protect the data integrity of the participants.

Table 2. Inclusion and Exclusion Criteria.

Inclusion Criteria

- Self-report as AA or Black
- English speaking
- History of BC (Stage I–IV); 3 months to 6 years post-adjuvant chemotherapy
- Participants on hormonal therapies or HER-2 therapy are acceptable

Exclusion Criteria

- Self-reported regular meditation or gratitude practices (more than once a week for at least a month)
- Meeting the CDC's physical activity guidelines (at least 150 min of moderate-intensity aerobic physical activity or 75 min of vigorous-intensity physical activity, or an equivalent combination each week)

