Blood-draw collection. Although generally safe, blood-draw collection procedures can confer limited risks, including that a participant will experience pain or discomfort. To minimize discomfort, we will make no more than two attempts per time point to obtain blood samples with any one participant.

Onsite adverse events. In the event of any of the following adverse events, we will immediately notify a physician and the IRB: 1) deaths, 2) falls, or 3) health events that result in immediate hospitalization or medical care.

Attrition. Given the success of the studies conducted at the UF OAIC Clinical Research Core, we do not expect any recruitment issues. However, since this proposal requires two visits to the institute, we are anticipating 5%–10% attrition. We will thus gather all primary data (blood draw and electronic questionnaires) during the T1 visit. At the T2 visit, we will collect another blood draw and the electronic questionnaires and conduct exit interviews and administer the CSQ to evaluate usability, usefulness, and participant satisfaction. Both structured and openended questions will be used to assess participants' perception of the intervention's content, value, structure, and burden. To further minimize attrition, we will (1) educate participants during the initial telephone screening about the importance of committing to the study, (2) obtain complete contact information (including alternative email addresses and phone numbers), (3) place a reminder call and/or email (if available) 2 days before the scheduled visit, and (4) provide compensation upon completion of each visit.

Inadequate Sample Size. Since this is a pilot feasibility study, which requires a relatively small sample, it may be underpowered to detect statistically significant differences in outcome measures. However, it will provide the information necessary to design future adequately powered efficacy studies.

Adequacy of Protections Against Risks

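### Aim 2's effect sizes and group tests should come from one baseline-adjusted analysis; the plan splits them between a change-type mixed model and t-tests on an unnamed variable

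*Combined protocol and SAP*

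**What the plan says.** Data Analysis plans a separate mixed model for each outcome, "comprised of effects for treatment, time, and treatment-by-time interaction, will be used to estimate effect sizes for each of the outcome variables". Box-Cox transformation is allowed where the model residuals call for it. On missing data it says "CONSORT guidelines for intent-to-treat principles will be used for hypothesis testing to manage missing data related to attrition", and the paragraph ends "We will determine differences between groups using t-tests". It does not say whether the t-tests are on T2 scores, on change or on a model contrast. It also gives no T1 covariate, no degrees-of-freedom method for the model, and no rule on which result governs.

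Table 1 schedules eight scale or biomarker outcomes at both T1 and T2: GQ-6, FACIT-Sp-12, PSS, G-SWS-Q, TNF-α, IL-6, GDF15 and CRP. The five-stage exercise-readiness measure is also taken at both visits. The satisfaction questionnaire is taken at T2 only.

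On timing, Data Collection and Study Procedures says "After baseline (T1) data collection, participants will be randomized to either the gratitude journaling intervention or attention control group", but also that "an electronic survey will be sent following completion of the first appointment". The Attrition paragraph says "We will thus gather all primary data (blood draw and electronic questionnaires) during the T1 visit". The Gratitude Intervention paragraph says "During the initial session, the Principal Investigator or research assistant will provide a journal kit", and the fidelity table describes a different journal for each arm.

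**The concern.** Aim 2's product is a set of between-arm effect sizes, and the section on inadequate sample size says the pilot is meant to inform the design of a powered trial. With 28 women every interval will be wide. T1 is already scheduled for these outcomes, so an analysis that conditions on it could narrow most of those intervals at almost no cost.

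Two methods with no rule between them also leave a choice open after the data are seen. How much that matters depends on what the t-tests are applied to, and on whether a transformation used in the model carries over to them.

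Baseline adjustment needs T1 to be measured before a woman knows her arm. The passages on visit order do not settle this.

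**Working it through.** **Inputs from the documents.** 14 per arm, 28 in total (Study Participants); 1:1 allocation; "we are anticipating 5%–10% attrition" (Attrition). The total of 28 can be reproduced from the 12 per group in the title of the cited sample-size reference: 12/0.90 = 13.3, rounded up to 14 per arm. No SD, effect size or correlation lies behind it, and the plan states no expected precision.

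**Assumptions.** T1-T2 correlation r from 0.3 to 0.9; equal T1 and T2 SDs, set to 1; complete data; two-sided 5% level.

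**Step 1: what the interaction estimates.** On complete data the treatment-by-time term equals the between-arm difference in mean change. A t-test on change therefore has the same estimate, while a T2 t-test differs from it by the chance T1 difference between arms.

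**Step 2: standard errors.** SE² = (2/n) × factor, with n = 14 per arm.
- T2 only: factor 1.
- Interaction or change: factor 2(1 − r).
- Baseline-adjusted: factor (1 − r²)(1 + 1/(2n − 4)) = (1 − r²)(25/24).

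The half-width is SE × t(26) = 2.056, or SE × t(25) = 2.060 when adjusted. Example at r = 0.5: the interaction gives √(0.1429 × 1) × 2.056 = 0.777; adjusted gives √(0.1429 × 0.75 × 1.0417) × 2.060 = 0.688.

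| r | T2 t-test | Interaction or change | Adjusted | Adjusted vs interaction |
|---|---|---|---|---|
| 0.3 | 0.777 | 0.919 | 0.758 | 18% narrower |
| 0.5 | 0.777 | 0.777 | 0.688 | 11% narrower |
| 0.7 | 0.777 | 0.602 | 0.567 | 6% narrower |
| 0.8 | 0.777 | 0.491 | 0.477 | 3% narrower |
| 0.9 | 0.777 | 0.347 | 0.346 | 0.3% narrower |

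If one woman per arm is lost (2/28 = 7%), the adjusted SEs at r = 0.3, 0.5 and 0.7 are 0.383, 0.347 and 0.286.

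**Step 3: break-even in SE.** Against T2 only: 1 − r² = 24/25, so r = 0.20. Against the interaction: 1 + r = 2 × 24/25 = 1.92, so r = 0.92. If the T2 SD is k times the T1 SD, the change factor is 1 + k² − 2rk and the adjusted factor is k²(1 − r²)(25/24). For k above 1 they cross at a lower r, about 0.78 for k = 1.1. The change factor exceeds k²(1 − r²) by (1 − rk)², which is never negative. So the adjusted SE can exceed the change SE by at most √(25/24) − 1, about 2%.

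**Step 4: conflicting verdicts.** In 40,000 simulated bivariate-normal trials per cell with a true effect of 0.5 SD, T2 and change t-tests disagreed at the 5% level in 22%, 26% and 34% of trials at r = 0.3, 0.5 and 0.7. With lognormal outcomes (log-SD 0.7 to 1.0, effect 0.5 SD on the log scale, r = 0.3 to 0.7), a log-scale interaction and a raw-scale change t-test disagreed in roughly 10% to 22%.

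**Step 5: check of the replacement.** In null simulations (5,000 trials per cell; complete data or one missing T2 per arm), regression of T2 on arm and T1 rejected in 4.7% to 5.4%. A common-baseline mixed model rejected in 7.0% to 7.6% with normal-theory tests and in 4.9% to 5.5% with Kenward-Roger. The two treatment estimates agreed to four decimals in all 30,000 trials, including the 15,000 with missing T2.

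**The case against.** The strongest reply is that this is an efficiency preference in a pilot whose plan already concedes low power. The interaction is valid, the feasibility criteria do not depend on it, and the gain shrinks to 3% at r = 0.8 and almost nothing at 0.9, with r unknown. All of that stands, and it limits the point to precision and to naming one governing analysis.

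The aims speak of improvement over time and of change from baseline, so a change-score reading of the t-tests is at least as natural as a T2 reading. That also stands: the 22% to 34% disagreement applies only if T2 scores are tested. The change reading does not rule out conflict, however, because the Box-Cox remedy is tied to the model and not extended to the t-tests.

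A reader might infer more than the documents support:
- **That T1 is ignored.** It is not; the model uses it as a response.
- **That the planned tests have inflated type I error.** Ordinary t-tests already carry small-sample degrees of freedom. The 7.0% to 7.6% belongs to the replacement mixed model if fitted without a correction.
- **That dropping women without T2 is the main fault.** The planned mixed model can keep them. In the adjusted analysis they add nothing to the treatment estimate when every woman has T1.
- **That T1 questionnaires are answered after allocation is known.** Randomization is placed after T1 collection, a survey sent after the appointment could still precede it, and the initial session is not expressly the T1 visit. The passages are unclear; they do not establish the error.

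**Conclusion.** The point holds as a loss of precision and an unnamed governing analysis, not as bias. Over r = 0.3 to 0.8 the planned interaction's interval could be 18% to 3% narrower with baseline adjustment. The gain is almost nil at r = 0.9, and there is a slight loss beyond about 0.92, or from a lower r if the T2 SD exceeds the T1 SD. Against a T2 t-test, adjustment gains for r above about 0.20.

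These sizes rest on assumed correlations, equal SDs at the two visits and complete data; the documents supply none of these. The ambiguity about the t-test variable is plain from the text and needs no assumption. The change is worth making because effect sizes are a stated aim, but it has no bearing on whether the pilot meets its feasibility criteria.

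**What to change.** 1. For each approximately continuous outcome measured at T1 and T2, name one baseline-adjusted analysis by randomized arm that gives both the effect size and the test. The simpler choice is T2 regressed on arm and T1, with its t-based 95% CI. The equivalent is a mixed model of T1 and T2 with a common T1 mean, unstructured covariance and Kenward-Roger inference; the correction is needed for that model. Report the number missing T2 by arm.
2. Apply any transformation at both visits and to both the estimate and the test.
3. Keep t-tests only for measures with no T1 value, such as the satisfaction questionnaire, and label them descriptive.
4. Reconcile the visit-order statements in Data Collection and Study Procedures, Gratitude Intervention and Attrition. State that all T1 measures, including the electronic survey, are completed before allocation is disclosed.
5. Leave the five-stage readiness measure out of the linear analysis and show a T1-by-T2 stage table for each arm.

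The cost is analysis wording and about one degree of freedom per model. If r were 0, the adjusted SE would be 0.386 against 0.378 for a T2 t-test. If the survey now follows disclosure, the visit order would also have to change.

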treated with chemotherapy using organic social media recruitment, flyers ,multiple specialized recruitment strategies from the OAIC Clinical Research Core - Claude D. Pepper Center Participant Registry (IRB201601352), UF Health Cancer Center Community-Partnered Cancer Disparities Research Collaborative (CDRC), UF Health Cancer Center Community Outreach and Engagement, UF Healthstreet, Integrated Data Repsitory and UF Consent2Share Registries. Potential participants will be screened for eligibility via telephone. Eligible participants will be English-speaking, self-reported AA/Black, postmenopausal women with a history of BC (Stage I–IV) who are 3 months to 6 years post-adjuvant chemotherapy. Women on hormonal therapies and anti-human epithelial receptor 2 (HER-2) therapy will be included. Exclusion criteria include self-reported regular meditation or gratitude practices (more than once a week for at least a month) or currently meeting the Centers for Disease Control and Prevention (CDC)'s physical activity guidelines. Women will be compensated \$100 within two time points for their participation.

Study Design: We will adhere to intervention fidelity using the five standard NIH recommendations for intervention fidelity: 1) design of the study; 2) intervener training; 3) treatment delivery; 4) treatment receipt; and 5) treatment enactment.

NIH Recommendations	Description of Treatment Fidelity (Both Arms)
Design of study	To reduce variability in outcome measurement, we will train our research assistant
	and research intern using a detailed intervention manual to instruct the participants
	on how to provide journaling education.
	The interventional manual will include detail on how to use the journal prompts specific to the treatment group (gratitude) and control group (general memories). The prompts are included in a custom-designed journal (i.e., a gratitude-specific journal and a general memory journal) with dates and prompt listed inside each journal. The journal will include 1-2 major physical activity goal page, and an exercise educational resource to promote exercise readiness and self-efficacy.
	Additional forms to be used for data collection will be appropriately designed to encourage the collection of good quality data. They will be user-friendly, self-explanatory, and clearly formatted.

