Feasibility Outcomes: The number of potential participants screened and enrolled will be tracked to evaluate recruitment and retention rates for the study. Participant adherence to the intervention will be calculated based on the journal logs. Exit interviews and the CSQ will be administered at T2 to evaluate the intervention's usability and usefulness and participant satisfaction with the study. The exit interview will comprise both structured and open-ended questions about the participants' perception of the intervention's content, value, structure, and potential burden.

Inflammation and Aging/Senescence Biomarkers: Following collection of the blood sample, the plasma will be separated, aliquoted, and stored at −80°C for later assay. A custom multiplex immunoassay panel for TNF-α, IL-6, and GDF15 (R&D Systems, Minneapolis, MN) will be analyzed using a MILLIPLEX® Analyzer 4.3 xPONENT System (Luminex Corp, Austin, TX). CRP will be measured via ELISA (R&D Systems) using a BioTek Instruments (Winooski, VT) Synergy™ HTX Multi-Mode Microplate Reader and analyzed via Gen5 Microplate Reader Software (Bio-Tek Instruments). Analyses have a minimal interassay coefficient of variation < 14.

Data Analysis

Distributions, including missing-data patterns and the presence of out-of-range values for all variables, will be examined using descriptive statistics appropriate for level of measurement. We will assess participant satisfaction using mean CSQ scores and exit interview questions. The CSQ will provide additional details regarding the gratitude and goal setting exercises, which will be used as an indicator of demand (criterion: > 80% of participants enrolled) and correlated with measures provided. Feasibility will be measured by the proportion of women who meet the inclusion criteria relative to the number of women approached (feasibility defined as > 75% women approached meeting criteria), percentage of participants completing baseline assessment measures (feasibility defined as > 80% of participants completing measures), and percentage of participants who complete baseline assessments completing post-intervention assessment (feasibility defined as > 80% of those who complete baseline assessments completing post-intervention assessments).

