The PI and research assistant will obtain informed consent, conduct participant screening, collect questionnaire data, monitor the experiment, implement the intervention, and ensure the safety of the participants. All procedures will be conducted by trained personnel. All persons responsible for the intervention will undergo thorough training. The laboratory is equipped with a telephone in case of an emergency, and in-house registered nurses (clinical research nurses) are also available. Emergency phone contacts will be posted in the laboratory's manual of operations, and all experimenters will be informed about who to contact in the event of emergencies. Participants will also be informed that multiple measures will be taken to ensure their safety. Participants may withdraw from the study at any time.

Description of Informed Consent. IRB approval will be obtained before participant recruitment begins. Potential participants will be administered a brief phone screening to assess their appropriateness for the study. During the call, they will receive a brief description of the study procedures, including information about the nature of the questionnaires and blood-draw collection and associated risks. If they agree to participate, the PI will review the details of the study with them and review the written informed consent in detail in a private research study exam room during the initial visit at T1. Women will participate in the study only after they provide verbal and written informed consent. The informed consent form will include standard information, including a description of the research protocol, the potential risks and benefits of participation, participant assurances, and contact information for the PI. Participants will also be informed that they can withdraw from the study at any time and that this will have no adverse impact on the study or their future medical treatment. Potential participants will be provided a copy of the informed consent form to review before being asked to sign. Informed consent will be documented via the participant's and investigator's signatures. A signed copy of the informed consent will be provided to participants during the initial visit.

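### The protocol says how adverse events are recorded and reported but schedules no question that would find falls, injuries or unplanned care between T1 and T2 (minor; cheap to fix)

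*Combined protocol and SAP*

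**What the plan says.** **Exposure.** Under Gratitude Intervention, the first session supplies "an educational physical activity brochure to assist in setting 1-2 physical activity goals during the study period". The fidelity table, whose description column is headed as applying to both arms, adds: "The journal will include 1-2 major physical activity goal page, and an exercise educational resource to promote exercise readiness and self-efficacy". Table 2 excludes women who already meet the CDC activity guidelines.

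**Content of T2.** Data Collection and Study Procedures says that T2 "will include the same measures as baseline excluding the demographic and cancer history questionnaires". The Attrition paragraph of section 6 lists the visit: "At the T2 visit, we will collect another blood draw and the electronic questionnaires and conduct exit interviews and administer the CSQ". Feasibility Outcomes describes the exit interview as structured and open-ended "questions about the participants' perception of the intervention's content, value, structure, and potential burden". Table 1 has no row for adverse events, falls, injury or health-care use.

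**Contact between visits.** The fidelity table says: "The study staff will provide a weekly email reminder to enter a journal entry at least twice a week". It also gives participants a staff number and email address for problems. Section 6 adds a reminder call and/or email 2 days before a visit.

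**Safety text.** Section 6, under a heading limited to onsite events, requires immediate notification of deaths, falls and health events leading to immediate hospitalization or care. The Data- and Safety-Monitoring Plan has events recorded on the IRB's online form. Serious and unexpected events go to the IRB within 5 working days. Less-serious events are to be monitored and reported in the annual review.

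**The concern.** Recording and reporting begin only once staff know of an event. The journaling and goal pursuit take place at home, and no scheduled contact is described as asking what happened there. If the final report shows no falls or injuries, a reader cannot tell whether none occurred or none was asked about. Analysis cannot recover this later.

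The stake is modest but real. The pilot is meant to inform a larger trial, and the Background describes older survivors as having cardiovascular disease and obesity. A basic count of falls, injuries and unplanned care is useful before activity goals are carried forward. A question at T2 comes after the exposure has ended, so its value is mainly to the next trial and only slightly to the protection of these participants.

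**Working it through.** The check is mainly a reading of every scheduled contact after T1, followed by a short calculation of what a solicited count could show.

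**1. Does any scheduled contact ask about harm?**

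| Contact | Stated content | Asks about falls, injury or unplanned care? |
|---|---|---|
| Weekly email | Journaling reminder | No |
| Call/email 2 days before visit | Visit reminder | No |
| T2 repeated measures (Table 1) | Gratitude, spiritual well-being, stress, superwoman schema, exercise readiness, biomarkers | No |
| T2 satisfaction questionnaire | Acceptability | No |
| T2 exit interview | Content, value, structure, burden | Not stated |
| Journal collected after week 8 | Number of entries, words per entry | Not stated |
| Staff number and email | Participant must initiate | No |
| General health information (Sources of Data) | Significant medical conditions; no time point | Not stated |

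None is specified as a safety question. The last four could bring an event to light incidentally.

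**2. Length of the unobserved period.** The intervention starts within 1 week of T1, and T2 falls 8 weeks after that start, so recall would cover about 8 to 9 weeks.

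**3. The plan's sample size.** The cited reference's title gives 12 per group. With the stated 10% attrition, 12 / (1 − 0.10) = 13.3, rounded up to 14 per group, or 28 in total. This reproduces the plan's figure, and nothing below changes it.

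**4. Women who would miss a question asked only at T2.** At the stated 5%–10% attrition, 28 × 0.05 = 1.4 and 28 × 0.10 = 2.8, so about 1 to 3 women.

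**5. What a solicited count could show.** With no events in n women, the exact (Clopper-Pearson) two-sided 95% upper limit is 1 − 0.025^(1/n). For n = 28 this is 12.3%, and for n = 14 it is 23.2%. With one event the limits come from the corresponding beta quantiles.

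| Women with an event | Exact 95% interval |
|---|---|
| 0 of 28 | 0% to 12.3% |
| 1 of 28 | 0.1% to 18.3% |
| 0 of 25 (about 10% not reached) | 0% to 13.7% |
| 0 of 14 (one arm) | 0% to 23.2% |
| 1 of 14 (one arm) | 0.2% to 33.9% |

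These intervals treat each woman's answer as correct. Without a question, that assumption has no basis in the plan. With one it is more plausible, though still imperfect.

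**The case against.** **Harms are captured only if volunteered.** A reader might infer this, but the documents do not go so far. The safety plan says that less-serious events will be monitored, without giving a method, and section 6 makes the PI and research assistant responsible for participants' safety. An open-ended interview, the burden topic or a journal entry could reveal an event; the control prompt asks about memorable events of the day. Table 1 is not exhaustive either, since it omits the exit interview. What stands is narrower: no active solicitation is specified.

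**Offsite events go unreported.** The onsite heading might suggest this. The Data- and Safety-Monitoring Plan's form and reporting tiers carry no onsite limit, so reporting is covered once an event is known.

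**Participants are not warned of activity risk.** The phone-screening description mentions "including information about the nature of the questionnaires and blood-draw collection and associated risks", but that wording is not an exhaustive list. For consent the protocol says: "The informed consent form will include standard information, including a description of the research protocol, the potential risks and benefits of participation". The form itself is not in the documents, so no such conclusion can be drawn.

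**True event rates could be several times higher than a zero count suggests.** That would require a figure for the share of events that come to light. The documents give none.

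**The point is too small to raise.** The component is light: a brochure and one or two goals, with no prescribed or supervised exercise. Asking also does not guarantee full capture, because recall is imperfect and some women will miss T2. If both arms receive goals, there is no goal-free comparator. All of this stands. It limits the severity but does not remove the gap.

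**Conclusion.** The point holds as a minor one. The protocol specifies recording and reporting of adverse events, but no active solicitation of events between T1 and T2. After 8 weeks of activity goals in women below the activity guidelines, a zero count would be hard to interpret.

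The conclusion rests on the protocol text alone. If the interview script or a study manual already contains the question, the sponsor need only say so in the protocol. Asking improves interpretability, not precision: even a complete count of 0 of 28 is compatible with a risk of up to 12.3%. No aim, effect estimate or sample size is affected.

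**What to change.** 1. At T2, ask both arms one question in identical words: since the first visit, has there been any fall, injury or unplanned medical care (yes/no, date, action taken)? Leave exercise and journaling out of the wording, so that it is neutral between arms. It can be an item in the T2 electronic questionnaire if staff are required to check the answer.
2. Phone women who miss T2 with the same question, using the contact details already planned for collection.
3. Handle each yes with the form and reporting tiers of the Data- and Safety-Monitoring Plan. Leave the onsite notification rule as it is.
4. In Data Analysis, add the number and percentage of women with at least one event, pooled and by arm, with exact 95% confidence intervals and no test.

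**Cost.** An IRB amendment, a few minutes at an existing visit, about 1 to 3 phone calls, follow-up of yes answers and more minor events to log. Recall over 8 to 9 weeks will miss some minor events, and the intervals will stay wide. By-arm counts may not isolate the activity component, because both arms may receive goals; the pooled count is the more useful one. Eligibility, sample size and number of visits do not change.
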